6.3.7. Impact of AECOPD on lung function

Descriptive statistics (N, mean, median, standard deviation, minimum and maximum) on post-bronchodilator FEV₁% of predicted normal value and PEF will be tabulated at enrolment and final visit. Change from baseline will be also summarized overall and represented according to the number of exacerbations.

6.3.8. Impact of AECOPD on healthcare utilisation

Descriptive statistics of the daily number of healthcare utilisation (number of HCU in the relevant period divided by the number of days) within the stable period and within the exacerbation period will be presented overall and divided by the following unscheduled visits:

1. Number of physician office consultations,
2. Number of visits to urgent care,
3. Number of visits to emergency department,
4. Number of hospitalizations.

Healthcare use for each patient will be obtained through review of the patient's medical record (aided by patient daily self-reporting in the eDiary).

Healthcare utilisation will be summarized according to country and COPD grade at enrolment. In addition, healthcare utilisation will be summarized by AECOPD severity during exacerbations.

Overall HCU [total number and divided by type of HCU] per patient will be correlated to the number of exacerbations experienced during the observation time.

Current medication for COPD and additional COPD treatments prescribed by primary and secondary care physicians within the stable period and within the exacerbation period will be described by drug category (chronic use for COPD and chronic use for other

CONFIDENTIAL

201112 (EPI-NTHI-001 BOD APA)
 Statistical Analysis Plan Amendment 2 Final

disorders) overall, by country and by COPD grade at enrolment. In addition, percentage of patients with or without inhaled corticosteroids at enrolment and incidence rate of confirmed exacerbation by use of corticosteroids will be tabulated.

6.4. Analysis of tertiary objective

The analyses of the tertiary objectives will be performed on the full analysis set.

6.4.1. End date of AECOPD using EXACT-PRO

Descriptive statistics (N, mean, median, standard deviation, minimum and maximum, first and third quartiles) on the average length of AECOPD episodes, as estimated through the EXACT-PRO (section 12), will be presented, for any, mild, moderate and severe AECOPD.

The frequency distribution of exacerbation confirmed at site visit or through medical records (with or without morning symptoms diary alert) will be tabulated versus EXACT-PRO exacerbations.

Descriptive statistics (N, mean, median, SD, minimum, maximum, first and third quartiles) for the EXACT daily scores will be tabulated at baseline, during the day before exacerbation, at exacerbation onset and at recovery according to investigator judgement. These statistics will be reported overall and for any mild, moderate or severe exacerbation visit.

Graphs detailing the EXACT-PRO scores before, during and after exacerbation onset as defined clinically will be also presented.

Difference from baseline, with 95% CI, of EXACT score measured at stable scheduled visit will be plotted.

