9.7. Analysis of tertiary objectives

Descriptive statistics (median, mean, range, standard deviation, first and third quartiles) on the end date of AECOPD as provided by the investigator or estimated by EXACT-PRO (via a specific algorithm which will be detailed in the Statistical Analysis Plan) will be presented.

Descriptive summaries of the quantity of specific bacteria at each scheduled [stable] and exacerbation visit will be provided for both culture and PCR analysis.

Descriptive summaries of the quantity of specific viruses at each scheduled [stable] and exacerbation visit will be provided for PCR analysis.

A conditional logistic model will be fitted to estimate the odds ratio of being in a stable state vs. an exacerbation state given the presence or not of several bacterial pathogens found by bacteriological culture and by country. The same model will also be performed for bacterial and viral pathogens found by PCR.

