3.3. Tertiary objectives

- To assess the use of EXACT-PRO for determining the end date of AECOPD.
- To evaluate the load of bacterial and viral pathogens in stable COPD and during AECOPD.
- To collect biological specimens for future respiratory disease-related testing:
 - Aliquots of sputum samples for assay development and microbiome analysis at stable visits and during exacerbation.
 - Blood sampling for potential biomarkers for identification/quantification of biomarkers at Visit 1 and Visit 3.

CONFIDENTIAL

201112 (EPI-NTHI-001 BOD APA)
 Statistical Analysis Plan Amendment 2 Final

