6.3.5. Severity and duration of AECOPD

Total number of exacerbations recorded during the study, exacerbation rate (number of exacerbation per patient-year) and the proportion of COPD patients experiencing a certain number of exacerbations will be presented overall and per bacterial/viral species. The exacerbation rate per year will be reported with and without correction for early withdrawal (see Section 11.3).

Total number of exacerbations recorded during the study, the mean exacerbation rate per year and the proportion of COPD patients experiencing a certain number of exacerbations will be presented overall and divided by AECOPD severity.

The number and proportion of COPD patients experiencing a certain number of exacerbations will be presented overall and by GOLD grade at enrolment.

CONFIDENTIAL

201112 (EPI-NTHI-001 BOD APA)
 Statistical Analysis Plan Amendment 2 Final

The number of patients that report at least 1 AECOPD will be tabulated and descriptive statistics (N, mean, median, SD, minimum, maximum, first and third quartiles) on the average length of AECOPD episodes, as estimated by the investigator, will be presented, for any, mild, moderate and severe AECOPD.

Number of days between 2 consecutive exacerbations, as estimated by the investigator, will be summarized using the same descriptive statistics.

Descriptive statistics of the number of patients according to their percentage of days within an exacerbation period out of the total observation period as estimated by the investigator will be presented. For this analysis, the exacerbations for which the end date was unknown were not excluded and the length was estimated by the investigator as the average length per severity grade.

Results from the chest X-rays during exacerbation visit will be tabulated.

The percentage of scheduled visit in which the status of the patient is stable/recovered, or not recovered will be tabulated.

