An EXACT-PRO AECOPD event is defined as a 12 point increase above baseline for 2 consecutive days, or a nine point increase for 3 consecutive days.

The baseline EXACT-PRO score is calculated as the average daily EXACT-PRO score over days 14 to 8 preceding AECOPD symptomatic onset.

AECOPD recovery according to EXACT-PRO corresponds to the day at which the EXACT-PRO score return to its baseline value (or below) [Mackay AJ, Donaldson GC, Patel AR, Singh R, Kowlessar B, Wedzicha JA. Detection and severity grading of COPD exacerbations using the exacerbations of chronic pulmonary disease tool (EXACT). *Eur Respir J*. 2014;43(3):735-44.].

The AECOPD duration according to EXACT-PRO will be defined as the number of days from AECOPD onset (included) and AECOPD recovery according to EXACT-PRO (not included).

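### No planned output measures, event by event, how many days apart the EXACT-PRO and investigator end dates of an AECOPD are, so agreement on the end date (a tertiary objective) is not quantified

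*SAP*

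**What the plan says.** SAP 3.3 states the objective: "To assess the use of EXACT-PRO for determining the end date of AECOPD". For this, Protocol 9.7 plans descriptive statistics "on the end date of AECOPD as provided by the investigator or estimated by EXACT-PRO" and leaves the algorithm to the SAP.

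The current SAP (Amendment 2) provides the following:

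- **EXACT-PRO length (6.4.1):** descriptive statistics "on the average length of AECOPD episodes, as estimated through the EXACT-PRO (section 12), will be presented", for any AECOPD and by severity.
- **Investigator length (6.3.5, under a secondary objective):** descriptive statistics "on the average length of AECOPD episodes, as estimated by the investigator, will be presented, for any, mild, moderate and severe AECOPD".
- **Cross-tabulation (6.4.1):** exacerbations confirmed at a visit or through medical records "will be tabulated versus EXACT-PRO exacerbations".
- **EXACT scores (6.4.1):** daily scores summarised at baseline, on the day before the exacerbation, "at exacerbation onset and at recovery according to investigator judgement", with graphs of the score around onset.

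SAP 12.2 sets EXACT-PRO recovery at the day the score is back at or below a baseline averaged over days 14 to 8 before onset. SAP 12.1 bases the investigator's end date on judgement, with diary symptoms taken into account.

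**The concern.** Whether EXACT-PRO can determine an end date depends on how far its date lies from the reference date in the same episode. Two length distributions shown side by side do not give that distance. Equal means and SDs are compatible with close agreement or with none.

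Even the difference between the two means is hard to read. The SAP does not require the tables to cover the same events, and its two duration rules can be a day apart. Following the plan exactly, the study report could show that the two methods give similar average lengths, but not how often they agree on when an episode ended.

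**Working it through.** **1. Does any planned output give the distance between the two end dates of one event?**

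- EXACT-PRO length table: no, one source only.
- Investigator length table: no, one source only.
- Cross-tabulation: compares the sources, but on occurrence and not on the end date.
- EXACT score at investigator recovery, beside the baseline score: bears on the end date, because SAP 12.2 defines EXACT-PRO recovery by return to baseline. It is a summary of scores and not of days.

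The documents give no agreement figure or sample-size figure for this objective, so there is no stated number to reproduce.

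**2. How much agreement do two identical length tables leave open?** Both lengths start at AECOPD onset. With one duration formula, the per-event difference in length is therefore the difference in end date. Assume that both methods have mean 14 and SD 10 days (the documents give no length distribution) and within-event correlation ρ:

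SD of difference = 10 × √(2(1 − ρ)); 95% limits of agreement = ±1.96 × that SD.

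- ρ = 0: SD 14.1, limits ±27.7 days
- ρ = 0.5: SD 10.0, limits ±19.6 days
- ρ = 0.9: SD 4.5, limits ±8.8 days

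**3. Check with skewed lengths.** A normal model with mean 14 and SD 10 would put about 8% of lengths below zero, so the check was repeated by simulation (400,000 pairs) with lognormal lengths, median 10 days and log-SD 0.6 (assumed). Both tables show mean 12.0, SD 7.9 and median 10 in every case. For a log-scale correlation of 1, 0.9, 0.5 and 0, the share of events with end dates within 2 days is 100%, 64%, 35% and 25%. Over the same correlations, median 7 with log-SD 0.5 runs from 100% to 40%, and median 14 with log-SD 0.7 from 100% to 16%.

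**4. Do the two tables rest on the same events?** They start from the same definition. SAP 12.4 counts AECOPD events plus missed visits with medical records in every analysis that uses no specimen. They can then diverge in three ways: missing diary data, no EXACT-PRO return to baseline (12.2), or partial or missing exacerbation dates, which SAP 11.3.1 leaves out of length.

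**5. The one-day mismatch.** The wording of SAP 12.1 and 12.2 excludes the recovery day, but the formula in 12.1 is recovery date minus onset date plus 1. Take onset on day 1 and recovery on day 11 by both methods. The EXACT-PRO length is 11 − 1 = 10 days; the investigator formula gives 11 − 1 + 1 = 11 days. Identical end dates then produce tables one day apart.

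**6. Precision of a paired summary.** Protocol 9.2 assumes 90% participation and on average 1 AECOPD visit, so 200 × 0.90 × 1 = 180 events, if each yields a pair. In units of the SD of the differences, the 95% CI half-width is 1.96/√n for the mean difference and 1.96 × √(1/n + 1.96²/(2(n − 1))) for each limit of agreement:

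- n = 180: 0.15 and 0.25
- n = 100: 0.20 and 0.34
- n = 40: 0.31 and 0.53

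These treat events as independent; repeated events within a patient would widen them.

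**The case against.** The best reply is that the plan offers more than two length tables. If investigator recovery often fell before the EXACT score was back at baseline, the scores at investigator recovery should tend to be higher or more spread than under close agreement. That table uses both criteria on the same events. This stands. A reader might infer that the plan contains nothing on the end date, or that the end date cannot be examined at all, and 6.4.1 does not support that. What is missing is a per-event measure in days.

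A reader might also infer that medical-record events enter only the investigator lengths, or that EXACT-PRO lengths require complete diary data for days 14 to 8. Neither is supported. SAP 12.4 applies to both tables. SAP 12.2 states no minimum coverage for the pre-onset baseline; the 4-of-7-day minimum in 12.2.1 concerns the enrolment baseline. Divergence between the tables is possible but not built into the definition.

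Finally, the objective is tertiary, Protocol 9.7 promises only descriptive statistics, and SAP 7 limits all analyses to supportive use or hypothesis generation. Nothing says that EXACT-PRO is meant to replace the investigator's date. This limits the weight of the point but does not answer it: limits of agreement and percentages within day bands are themselves descriptive. SAP 6.3.1 already reports an agreement statistic with its CI for PCR against culture.

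**Conclusion.** The point holds in this form: the plan does not quantify, per event, agreement between the EXACT-PRO and investigator end dates, which is what the tertiary objective is about. Under the assumed mean of 14 and SD of 10 days, the same pair of length tables is compatible with limits of agreement from ±8.8 to ±27.7 days. These figures show what the tables leave open and do not predict disagreement. Correlation 0 is an extreme case, since both lengths share an onset and the investigator also considers diary symptoms. For the same reason, the investigator's date is not a fully independent reference.

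The change is worth making because it is cheap. The missing comparison leaves primary and secondary results unaffected. The duration mismatch is a separate matter of wording; settling it may move the investigator lengths in SAP 6.3.5 by a constant one day.

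**What to change.** Add to SAP 6.4.1:

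> For each AECOPD with both end dates, the difference in end date (EXACT-PRO minus investigator, days) will be summarised descriptively by mean with 95% limits of agreement, median, quartiles and percentage within pre-stated day bands (e.g. ±3 and ±7), overall and by severity, with CIs allowing for repeated events per patient. AECOPD with no computable EXACT-PRO baseline or no EXACT-PRO recovery will be counted separately.

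In addition:

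- Show both length tables on this common set of events as well.
- Reconcile the formula in SAP 12.1 with the wording of 12.1 and 12.2, and use one duration formula for both methods.
- State that the investigator's end date draws on the diary and is not independent of it.

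The day bands are examples; the team should fix its own before the analysis. The cost is SAP wording, one derived variable and the resulting tables, with no new data.

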6.4.2. Mixed infections

The simultaneous bacterial [culture/PCR] and viral presence in sputum at enrolment, any stable and any exacerbation visit [mild, moderate, severe] will be computed overall and by pathogens.

6.4.3. Load of bacteria and virus

Total number of patients providing a sputum sample, the number of sputum samples positive to specific bacteria (by culture) and the frequencies of semi-quantitative bacteriological load (few scattered, +, ++, +++) will be tabulated at each scheduled [stable] visit and at each exacerbation visit.

Total number of patients providing a sputum sample, the number of sputum sample positive to specific bacteria (by PCR)/HRV and average load will be tabulated at each scheduled [stable] visit and at each exacerbation visit.

CONFIDENTIAL

201112 (EPI-NTHI-001 BOD APA)
 Statistical Analysis Plan Amendment 2 Final

6.4.4. Impact of occurrence of bacterial/viral pathogens in sputum on AECOPD

The following proportions and 95% CIs will be computed:

- Proportion of sputum samples which are positive for specific pathogens [NTHi, Mcat, S. pneumoniaeP. aeruginosa, K. pneumoniae, HRV] at an AECOPD visit but not at the previous stable visit and proportion of sputum samples which are positive for specific pathogens [NTHi, Mcat, S. pneumoniae, P. aeruginosa, K. pneumoniae, HRV] at an AECOPD visit but not at the previous visit (either stable or AECOPD visit) (apparition).

Proportion of sputum samples which are positive for specific pathogens [NTHi, Mcat, S. pneumoniae, P. aeruginosa, K. pneumoniae, HRV] which appeared for the first time, during the study, at an AECOPD visit (acquisition). For both acquisition and apparition, the CIs will be estimated using a GEE model assuming a binomial distribution for the response variable with logit as link function and a compound symmetry correlation matrix (exchangeable structure) to account for the within-patient correlation.

In addition to these proportions the following odds ratios (ORs) will be calculated:

- Odds of experiencing an AECOPD (vs. being in a stable state) for patients with sputum positive for selected pathogens (vs. those with negative sputum)
- Odds of experiencing an AECOPD (vs. being in a stable state) for patients with sputum positive for selected pathogens for the first time during the study (acquisition) vs. those without acquisition
- Odds of experiencing an AECOPD (vs. being in a stable state) for patients with sputum positive for selected pathogens which was negative at the previous visit (apparition) vs. those without apparition

To obtain the odds ratios conditional logistic regression models, stratified by patient, will be fitted. Separate analyses considering bacteria detected by culture and PCR as well as viruses detected by PCR will be conducted. For each analysis, three models will be run: the first will include the pathogen, season and the interaction term between the pathogen and season, the second will include the pathogen and will be adjusted for season (without the interaction term) and the third will only include the pathogen. Season will be treated as a dichotomous variable with high season (October to March) and low season (April to September)..

The conditional logistic model allows estimating the impact of independent variables from observations from each individual patient. In other words, by stratifying by patient, there is no need to adjust for time-invariant covariates such as age and sex.

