4.3. Exclusion criteria for enrolment (Amended 19 October 2018)

Deviations from exclusion criteria are not allowed because they can potentially jeopardise the scientific integrity and regulatory acceptability of the study or subject safety. Therefore, adherence to the criteria as specified in the protocol is essential.

The following criteria should be checked at the time of study entry. If ANY exclusion criterion applies, the subject must not be included in the study:

- Diagnosed with a respiratory disorder other than COPD (such as sarcoidosis, active tuberculosis or receiving tuberculosis treatment, clinically significant bronchiectasis, lung fibrosis, pulmonary embolism, pneumothorax, lung cancer diagnosed within the previous 5 years, current primary diagnosis of asthma in the opinion of the investigator), or chest X-ray revealing evidence of clinically significant abnormalities not believed to be due to the presence of COPD*. Subjects with allergic rhinitis do not need to be excluded and may be enrolled at the discretion of the investigator.

** A chest X-ray must be taken at Screening Visit, if no chest X-ray taken within the previous 3 months is available.*

- Diagnosis of α -1 antitrypsin deficiency as the underlying cause of COPD.
- Undergone or has had lung surgery 12 months before, or plans to have lung surgery 12 months after, study entry.
- Any confirmed or suspected immunosuppressive or immunodeficient condition, based on medical history and physical examination (no laboratory testing required).
- Received chemotherapy within the 12 months before study entry.
- Concurrently participating in another clinical study, at any time during the study period, in which the subject has been or will be exposed to an investigational or a non-investigational vaccine/ product (pharmaceutical product or device).

- Administration of antibiotics within 1 month of study entry OR continuous administration of antibiotics (defined as more than 30 days in total) within 90 days before study entry*.

**** Study entry is Visit 1. If this exclusion criteria is met during Screening Visit the patient can enter the study and this exclusion criteria will be reassessed during Visit 1.***

- Systemic administration of corticosteroids (PO/IV/IM) for more than 14 consecutive days within 90 days prior to informed consent.

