6.4.3.9. Sputum sampling (Amended 19 October 2018)

- Sputum samples during AECOPD should preferably be obtained before administration of the first dose of antibiotics to treat the AECOPD (if applicable). Sputum can be collected spontaneously or can be induced, as per investigator judgement. Sputum sampling should only be done if, in the opinion of the investigator, it is safe for the subject.

- Sputum sample collected at subject's home (spontaneous): Self-collection of the sputum sample will be allowed in specific cases, where the first dose of antibiotics absolutely needs to be taken before an AECOPD visit can take place. This is not allowed at scheduled visits when subject should be in stable condition.
- Collected sputum will be diluted in DTT, processed and cultured within 6hrs of collection for microbiology testing.
- Remaining DTT-sputum will be aliquoted as such. These samples will be kept at -70/80°C until shipment to GSK or GSK designated lab for testing.

Refer to the SPM and the Central Laboratory Investigator Manual for more details and guidance on handling of sputum samples.

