6.3.3. Sputum sample collection and quality

6.3.3.1. Sputum sample collection

The percentage of patients at each scheduled [stable] and exacerbation visit for whom a sputum sample is obtained will be computed overall and by the method the sample is obtained [i.e. spontaneous (at study visit or at patient's home), induced using 0.9% saline or induced using 3% saline]. The percentage of patients with induced sputum will be tabulated by GOLD grade at enrolment and by severity of the AECOPD. The proportion of sputum samples obtained at each confirmed stable or AECOPD visit [any, mild, moderate and severe] with or without induction and positive for specific bacterial\viral pathogens by bacteriological culture and bacterial\viral PCR will be computed.

The distribution of the number of sputum samples will be presented according to time (days) since the start of exacerbation. The distribution of the proportion of sputum sample positive for bacteria/virus given the number of days between the start of exacerbation and sample collection will be presented.

CONFIDENTIAL

201112 (EPI-NTHI-001 BOD APA)
 Statistical Analysis Plan Amendment 2 Final

The impact of previous antibiotic administration on bacterial results presence will be evaluated. The proportion of sputum samples obtained at each confirmed stable or AECOPD visit [any, mild, moderate and severe] with previous administration of antibiotics or not and positive for specific bacterial pathogens by bacteriological culture and PCR, respectively will be computed.

The impact of previous vaccination with a pneumococcal vaccine or an influenza vaccine (regardless of time) on *S. pneumoniae* and influenza virus will be evaluated. The proportion of sputum samples obtained at each confirmed stable or AECOPD visit with previous vaccination or not and positive for *S. pneumoniae*, by culture and PCR or influenza virus, by PCR, will be computed.

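### The AECOPD-versus-stable odds ratios in SAP 6.4.4 take no account of antibiotics taken before the sample; a restricted refit with one common look-back window would show how much this matters

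*SAP*

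**What the plan says.** **The models.** SAP 6.4.4 defines three odds ratios of exacerbation versus stable state: for a positive sputum, for a first positive during the study, and for a positive after a negative previous visit. "To obtain the odds ratios conditional logistic regression models, stratified by patient, will be fitted", separately for bacteria by culture, bacteria by PCR and viruses by PCR. Each analysis has three models. The first contains pathogen, season and their interaction; "the second will include the pathogen and will be adjusted for season (without the interaction term) and the third will only include the pathogen". The section adds that, because of the stratification, "there is no need to adjust for time-invariant covariates such as age and sex". Protocol 9.7 plans the same type of model, also without an antibiotic term.

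**The sampling rules.** At an exacerbation the visit may be up to 96 hours after onset. Protocol 6.4.3.9 says: "Sputum samples during AECOPD should preferably be obtained before administration of the first dose of antibiotics to treat the AECOPD (if applicable"). It also provides a mitigation: "Self-collection of the sputum sample will be allowed in specific cases, where the first dose of antibiotics absolutely needs to be taken" before the visit. Protocol 4.3 excludes patients given antibiotics within a month of study entry and defines study entry as Visit 1. No matching rule exists for Visits 2 and 3. A stable visit that coincides with an exacerbation is moved until the patient is stable again (Protocol 3.1.1 and Table 6), with no antibiotic-free interval stated.

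**Antibiotics elsewhere in the SAP.** Section 6.3.3.1 tabulates samples, at stable and AECOPD visits alike, "with previous administration of antibiotics or not and positive for specific bacterial pathogens by bacteriological culture and PCR", but gives no time window for previous administration. Code 2040 in 5.4.4 names antibiotics as affecting the primary endpoint, and leaves removal of samples to case-by-case judgement. Section 6.2 allows patients on continual antibiotics to be left out.

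**The concern.** Conditioning on the patient removes what is constant within a patient. Whether an antibiotic preceded a given sample is not constant, and it can follow from the exacerbation itself: a moderate event is defined by treatment with systemic corticosteroids and/or antibiotics (Protocol Table 2). If antibiotics lower culture yield, the exposure is measured differently in the two states being compared. This is misclassification that depends on the outcome rather than ordinary confounding.

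At stake is the reading of a culture-based odds ratio near 1. It could mean that the bacterium is unrelated to exacerbation, or that treated exacerbation samples grew less. As specified, 6.4.4 cannot separate the two, and the only way to remove affected samples is a judgement made case by case.

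**Working it through.** **1. The plan's own figures.** The documents state no expected odds ratio. The nearest figure is the AECOPD sample count in Protocol 9.2: 200 x 0.9 x 1 x 0.8 = 144, stated as around 140. The exact 95% interval for 20% of 140 (28/140) is 13.7 to 27.6, as in Table 12.

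**2. What the documents allow before each type of sample.**
- AECOPD visit: antibiotics possible; sampling first is preferred; home collection in specific cases.
- Visit 1: no antibiotics in the previous month.
- Visits 2 and 3: no rule. Protocol 9.6 and SAP 6.3.3.1 both foresee previous antibiotics at stable visits.

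Greater exposure at AECOPD is therefore plausible but not established.

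**3. Formula.** Let p0 and p1 be culture positivity without antibiotics when stable and at AECOPD, f and g the shares of AECOPD and stable samples taken after antibiotics, and L the relative loss of detection after antibiotics. With odds(p) = p/(1 - p):

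observed OR = odds(p1(1 - fL)) / odds(p0(1 - gL)), where odds(p1) = true OR x odds(p0).

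The documents give none of p0, p1, f, g or L; all are assumptions. The formula is a marginal approximation to the conditional model.

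**4. No exposure before stable samples (g = 0), p0 = 0.30, true OR 2.** odds(p0) = 0.4286, odds(p1) = 0.8571, p1 = 0.4615.
- f = 0.2, L = 0.3: 0.4615 x 0.94 = 0.4338; odds 0.7663; OR = 0.7663/0.4286 = 1.79.
- f = 0.4, L = 0.6: 0.4615 x 0.76 = 0.3508; odds 0.5403; OR = 0.5403/0.4286 = 1.26.

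Over the same range a true OR of 1 becomes 0.92 to 0.69, and a true 3 becomes 2.62 to 1.74.

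The estimate falls below 1 only if f > (1 - p0/p1)/L. For a true OR of 2 and L = 0.6 this is 0.35/0.6 = 58% of AECOPD samples. For L = 0.3 it is 0.35/0.3, above 100%, so it cannot happen.

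**5. Some exposure before stable samples.**
- p0 = 0.30, f = 0.2, L = 0.3, g = 0.2: stable positivity 0.30 x 0.94 = 0.282; odds 0.3928; OR = 0.7663/0.3928 = 1.95 instead of 1.79.
- p0 = 0.20, L = 0.5, true OR 2, f = 10%: 1.85 at g = 0, 1.98 at g = 10%, 2.11 at g = 20%.
- The same with f = 30%: 1.58, 1.69 and 1.80, reaching 2.24 at g = 50%.

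**6. Simulation of the patient-stratified model.** Settings: 180 patients, three stable visits, Poisson(1) AECOPD visits, 80% of these sampled, random intercept SD 1.5, true OR 2, f = 30%, L = 0.5, g = 0. The median OR was 1.46 with all samples and 1.96 with samples free of prior antibiotics. The standard error of the log OR rose from 0.29 to 0.33. With g = 20% the medians were 1.67 and 2.02.

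Adding an antibiotic covariate instead failed when no stable sample was exposed: coefficient 14.8 with standard error 26.4, a sign of separation.

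**The case against.** The strongest objection is that the documents do not show exposure to be one-sided. The one-month exclusion protects only one of the three stable visits analysed. Visits 2 and 3 may follow a treated exacerbation, and both documents expect some stable samples after antibiotics. This stands: step 5 shows that such exposure shrinks the bias and can cancel or reverse it.

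Home self-collection is aimed at this very problem and will keep some AECOPD samples free of antibiotics. That stands in part, since it is reserved for specific cases and sampling first remains a preference.

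A reader might infer that the plan ignores antibiotics altogether. It does not: 6.3.3.1 splits positivity by previous antibiotics, continual users may be left out, and code 2040 allows samples to be dropped. None of these sets a rule for the odds-ratio models or corrects them.

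Restriction has its own weakness. It may remove treated and possibly more bacterial exacerbations, so the restricted estimate is not simply the right one. That stands, and is why both results should be shown.

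Finally, the odds ratios are tertiary, and SAP 7 limits all analyses to supportive use or hypothesis generation. This limits the importance of the point, but not its validity.

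**Conclusion.** The gap is real: the culture-based odds ratios in 6.4.4 leave out a time-varying influence that the SAP itself recognises and that patient stratification does not remove. The direction is conditional. If exposure before sampling is more common at AECOPD than at stable visits, the estimates are too low. A true 2 becomes 1.79 to 1.26 under 30% stable positivity, no stable exposure, 20-40% AECOPD exposure and a 30-60% loss of detection. These inputs are assumptions, and the no-stable-exposure case is the least favourable to the plan. The figures are for culture; no size is derived for PCR.

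Two stronger readings are not supported. A reader might infer that the associations are bound to be pulled to 1 or below. In these calculations that needs a null or weak true association, or heavy exposure at AECOPD. A reader might also infer that the primary AECOPD proportions go unexamined for antibiotics. Protocol 9.6 and SAP 6.3.3.1 already split them; what is missing is the window. The point is a cheap improvement to a hypothesis-generating analysis.

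**What to change.** 1. Define antibiotic before sample once, as antibiotic use within a fixed look-back window ending at sampling, with the same window at AECOPD and stable visits. Different windows would themselves classify the two states differently. Derive it from the recorded medication (Protocol 6.4.2.10 and 6.4.3.6). Those sections do not mention dose timing, so state how a dose and a sample on the same day are handled.
2. Use this definition for the split in SAP 6.3.3.1. A separate repeat of 6.2 is then largely unnecessary.
3. In 6.4.4, pre-specify a sensitivity analysis that refits the culture models, with the bacterial PCR models alongside, on samples without antibiotic before sampling at either visit type. Report it beside the all-sample models, with the number of samples and patients contributing to each.
4. Do not use an antibiotic covariate instead, because it may be inestimable when few or no stable samples are exposed.

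The cost is SAP wording, one derived variable and one more run of existing models. There will be fewer AECOPD samples, and a patient left without samples in both states no longer contributes. The standard error grows somewhat (0.29 to 0.33 in the simulated case), and the restricted set may lean towards milder or untreated events. The result stays tertiary and hypothesis-generating. Nothing changes in treatment or sampling.
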